4.4 Schedule of Assessments

4.4.1 Study Schedule A: Social Media Recruitment Path

Table 2: Schedule of Assessments for Social Media recruitment path only

	Remote Data Recording (via study website)	Central Reader Validation	Phone contact for scheduling clinic visit
Visits	V0		
Days		Within 2 working	Within 1 week after C.
		days from V0	Reader validation
Online pre-screening consent	X		
Contact details, demographics, health	X		
related behaviour			
Medical and surgery history questionnaire	X		
Concomitant medications questionnaire	X		
Face images upload	X		
Preliminary compliance with		Х	X
inclusion/exclusion criteria			
Study description to the subject			X
Decision recording			Х
Appointment set-up			Х

4.4.2 Study Schedule B: Social Media and On-site Recruitment Paths

Table 3: Schedule of Assessments for Social Media and On-site recruitment paths

	Screening Period	Baseline/ Randomization Visit	End of Treatment Visit	End of Study Visit	Early Termination Visit	Unschedul ed Visit
	V1	V2	V3	V4	ETV	UV
Days	-30 to -1	1	30 (±1)	60 (±3)	From 1 to 60	From 1 to 60

Written informed consent	X					
Demographics collection	Х					
and health-related						
behaviour assessment						
Relevant rosacea-	Х					
associated medical history						
Relevant non-rosacea-	Х					
associated medical history						
Previous and Concomitant	Х	Х	X	Х	Х	Х
medications	X		^		^	
Adverse events collection	Х	Х	×	X	X	Х
Vital signs (heart rate,	X	X	X	X	X	X
blood pressure, body			^		^	
temperature)						
		V				
Weight, Height* and BMI		X	X	V	X	V
Complete Physical	X	X	X	X	X	X
Examination		v		V		V.4
Rosacea-associated facial	X	X	X	X	X	X4
inflammatory lesion count (papules and pustules)						
Five-points Investigator's	X	Х	х	Х	Х	X4
Global Assessment (IGA)						
of Rosacea Severity						
Evaluation of erythema,	X	X	X	X	X	X4
telangiectasia, ocular manifestations and						
phymatous changes						
Visual Analogue Scale	X	Х	Х	Х	Х	X4
(VAS) for pain,						
burning/stinging and itching						
Abdominal symptoms						
questionnaire (IBS-SSS)1					→	
Dermatology Life Quality						
Index Questionnaire1					\longrightarrow	
Clinical chemistry,	X		Х	X	X	X4
haematology, urinalysis	^		^		^	, A4
Contraception		X				
recommendations and/or		^				
adherence^						
Serum pregnancy test^	X					
						 
Urine pregnancy test^		Х	X	Х	X	X4
						 
Lactulose Breath test	Х		Х		X	X4
Inclusion/exclusion criteria	Х	Х				
						1

Randomization	Х			
Blood sampling for PK analysis^^	X2	X3		
Ovemight stay^^		Х		
Drug dispensing	Х			
Drug accountability		Х	Х	

^{*}Height will be recorded at V1 only;

4.5 Sample Size

The sample size estimation is based on the co-primary efficacy endpoints, i.e. mean change from baseline in number of inflammatory lesions and percent of patients showing treatment success.

[^]Women of child-bearing potential only;

^{^^} Only in subjects participating in the PK sub-study;

¹To be collected every 10 days, starting from V2 up to V4, and recording patient's responses through anelectronic diary (ePRO).

 $^{^2}$ Sampling to be performed right before and after the first morning dose of Rifaximin-EIR at V2 (Day 1) at the following time points: immediately pre-dose and at 0.5, 1, 1.5, 2, 3, 4, 6, 8 hours post-dosing.

³Sampling to be performed right before and after the morning dose of Rifaximin-EIR on day 30 at the following points: immediately predose and at 0.5, 1, 1.5, 2, 3, 4, 6 and 8, 12, 22, 24, 30 hours post-dosing (singledose at Day 30). The sampling started at V3 (Day 30) and will end after overnight stay, as appropriate.

⁴ If judged necessary by the Investigator

The total sample size (153) was adjusted to 171 patients (57 in each treatment group) considering an expected dropout rate of about 10% (using Freedman's formula n'= 100*n/(100-x), where x is the expected dropout rate).

The initially planned sample size has been increased to a total of 201 patients (67 in each treatment group) to mitigate the impact on the statistical power of the treatment kit misallocation that occurred for 15 patients out of the initial 30 patients randomized. A cap of 33 subjects per arm having a negative L-BT result at screening (i.e., a test showing an increase ≤10 ppm of H2 by 90 minutes compared to time 0) is established.

Sample size for the sub-study on PK is not based on formal statistical assumptions. Initially, a cap of 12 PK subjects per study arm was established. This is considered a good value for this kind of study. In any case, in order to have an adequate sample size, the study requires at least 6 PK subjects per study arm. During the course of the study, the cap has been increased to 19 due to the failure to comply with the previous limit.

5 General Considerations

5.1 Presentation

Individual patient data obtained from electronic case report forms (eCRFs), central laboratories, local laboratories, external sources, and derived data will be presented in data listings by patient. All data listings that contain an evaluation date will contain a relative study day.

All outputs will be incorporated into Microsoft Word rich text format (.rtf) files, sorted and labeled according to ICH recommendations, and formatted to the appropriate page size(s).

Tabulations will be produced for appropriate demographic, baseline, efficacy, safety, rifaximin plasma concentrations and pharmacokinetic parameters. Tabulations will be organized by using column for each treatment group, and rows for each parameter and visit (or time) where appropriate.

For categorical variables, summary tabulations of the number and percentage of patients within each category (with an "unknown" category for missing data) of the parameter will be presented. Denominators for percentage calculations will include missing data, unless otherwise specified in the table description. Percentages are rounded to 1 decimal place, unless otherwise specified in the table shell.

For continuous variables, the number of patients, mean (arithmetic), SD, median, interquartile range (IQR), minimum, and maximum values will be presented. The precision of summary statistics, unless otherwise specified, will be as follows: mean, median, and IQR to 1 more decimal place than the raw

data and SD to 2 decimal places more than the raw data. In general, the decimal places should not exceed 3 decimal places unless appropriate. Cls will be provided and will be rounded to 1 more decimal place than the raw data, unless otherwise specified in the table and listing shell.

For ordinal variables, the summary procedures for both categorical and continuous variables will be followed where appropriate.

5.2 Data Conventions

The precision of original measurements will be maintained in summaries, when possible.

For tables where rounding is required, rounding will be done at the final stage of the calculation to the nearest round-off unit. For example, when rounding to the nearest integer, values $\ge XX.5$ will be rounded up to XX + 1 (eg, 97.5 will round up to 98), while values $\le XX.5$ will be rounded down to XX (eg, 97.4 will be rounded down to 97).

For frequency counts of categorical variables, categories whose counts are zero will be displayed for completeness. For example, if none of the patients discontinue due to "lost to follow-up," this reason will be included in the corresponding table with a count of 0. Percentages based on frequency counts of case report form (CRF) collections (eg, demographic categories) will be presented to one decimal place.

Quantitative laboratory tests containing less than (<) and greater than (>) symbols are test results that are below and above quantifiable limits, respectively. In order to retain these values for analysis purpose, values will be imputed as the numeric portion of the result.

5.3 Timing of Analyses

The statistical analyses will be performed at the end of the study, after the database has been cleaned and locked.

5.4 Analysis Populations

Study populations definitions are provided below. The numbers of subjects in each population and reasons for exclusion will the summarized.

All decisions on populations will be taken during a Blind Data Review Meeting and will be detailed in the relevant documents.

The analyses of the main efficacy endpoints will be performed on the FAS and the PP set. Results on the FAS will be considered primary. Results on the PP set will be used as supportive. The mFAS population will be used for sensitivity analyses. For details as to which populations will be used to analyze each endpoint please refer to the TLF Shells document.

5.4.1 Screened Population

Screened Population is defined as all subjects enrolled into a screening period after informed consent. A screen failure is defined as a subject who has not been randomized to treatment. Data from screen failures will only be listed as indicated.

5.4.2 Randomized Population

The randomized population is defined as the set of all randomized subjects.

5.4.3 Safety Analysis Set

All safety and tolerability analyses will be carried-out in the Safety Analysis Set (SAF), consisting of all randomized subjects having received at least once the investigational treatment.

Analysis on the SAF will be performed according to the actual treatment received.

5.4.4 Full Analysis Set

The primary efficacy analysis population will be the Full Analysis Set (FAS), defined as all randomized patients having taken at least one dose of the investigational treatment and have at least one post baseline assessment for any of the two co-primary endpoints.

To mitigate the impact of the treatment kit misallocations, the primary statistical analysis on the FAS will be performed according to the actual treatment received (not according to the "randomized" treatment, as per ITT principle).

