10.3 Method of Assigning Subjects to Treatment Groups / Randomisation

A unique subject's identification number will be assigned to all subjects consenting to be enrolled in the study obtained concatenating the center number with the screening number.

A subject who fails to meet the protocol eligibility criteria will be identified as screening failure; his/her identification number will not be reallocated.

Randomisation will occur at visit V2 after all baseline procedures have been performed and eligibility for the study has been confirmed.

Participants will be randomised, on a 1:1:1 basis, to Rifaximin-EIR 250 mg three times a day (750 mg daily) for 29 consecutive days and Rifaximin-EIR 250 mg single dose on Day 30, Rifaximin-EIR 500 mg three times a day (1500 mg daily) for 29 consecutive days and Rifaximin-EIR 500 mg single dose on Day 30, or placebo for 30 consecutive days.

Blocks will be used to assure treatment balance.

Patients will be stratified at randomization based on their L-BT status (negative vs. positive) and PK sub-study participation (yes or not).

Randomization will occur throughout an IWR system integrated into the e-CRF.

At V2, the randomization system will assign an individual Patient's kit number based on a pre-defined randomisation list.

The enrolment will be competitive.

Decoding of randomization in case of emergency is described in chapter 11.4.

The subjects will be offered participation to the PK sub-study. If they agree, they will be randomized according to the relevant stratum maintaining treatment balance among groups; otherwise, they will enter the main study.

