10.6 Blinding

Blinding is intended to limit the occurrence of conscious and unconscious bias in the conduct and interpretation of a clinical trial arising from the influence which the knowledge of treatment may have on the recruitment and allocation of subjects, their subsequent care, the attitudes of subjects to the treatments, the assessment of end-points, the handling of withdrawals, the exclusion of data from analysis, and so on.

In accordance with the double-blind design, both the Investigator and the patient will be unaware of the treatment being dispensed in each case. The placebo will be indistinguishable from the active substance, i.e. will have the same weight, appearance, colour, smell and flavour.

Only in case of an emergency, when knowledge of the study medication is essential for the patient's safety, the Investigator may unblind a patient's treatment assignment (see section 11.4 "Decoding of randomisation in case of emergency").

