16.1 Determination of Sample Size

The sample size estimation is based on the co-primary efficacy endpoints, i.e. mean change from baseline in number of inflammatory lesions and percent of patients showing treatment success.

Based on these assumptions, 51 patients were to be enrolled in each treatment arm as shown in the tables below.

CCI			

The total sample size (153) was adjusted to 171 patients (57 in each treatment group) considering an expected dropout rate of about 10% (using Freedman's formula (Control Clin Trials, 1990): n'= 100*n/(100-x), where x is the expected dropout rate).

The initially planned sample size has been increased to a total of 201 patients (67 in each treatment group) to mitigate the impact on the statistical power of the treatment kit misallocation that occurred for 15 patients out of the initial 30 patients randomized. A cap of 33 subjects per arm having a negative L-BT result at screening (i.e., a test showing an increase \leq 10 ppm of H₂ by 90 minutes compared to time 0) is established.

Sample size for the sub-study on PK is not based on formal statistical assumptions. A cap of 12 subjects per arm is established. This is considered a good value for this kind of study. In any case, in order to have an adequate sample size, it is advisable to have at least 6 subjects per arm.

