16.2.3 Full Analysis Set (FAS)

The primary efficacy analysis population will be the Full Analysis Set (FAS), defined as all randomised patients having taken at least one dose of the investigational treatment.

To mitigate the impact of the treatment kit misallocations, the primary statistical analysis on the FAS will be performed according to the actual treatment received (not according to the "randomized" treatment, as per ITT principle).

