16.3 Statistical and Analytical Plans

The statistical analyses will be performed at the end of the study, when the data base has been cleaned and locked.

The primary statistical analysis on the FAS will be performed according to the actual treatment received.

In addition, two sensitivity analyses will be implemented for the primary analysis:

- The first by analyzing the FAS according to the "randomized treatment", as originally planned
- The second on the mFAS according to the "randomized treatment".

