3.2 Study Endpoints

3.2.1 Co-primary efficacy endpoints

The following co-primary efficacy endpoints will be clinically assessed by the Investigator:

- 1. Change from baseline in number of rosacea inflammatory lesions (papules and pustules) at the end of treatment (Day 30)
- Percent of subjects showing treatment success, defined as an IGA score of 0 (clear) or 1 (almost clear), with at least a 2-grade improvement from baseline to the end of treatment (Day 30).

Success of the study will be declared in any of the active treatment groups if both the co-primary efficacy endpoints will be satisfied (note: the two items may not necessarily occur in the same patient).

Table 1. Investigator's Global Assessment (IGA) Score

Grade	Description	Amount and size of inflammatory lesions present
0	Clear	None
1	Almost Clear	Very few, small papules /pustules
2	Mild	Few small papules/pustules
3	Moderate	Several small or large papules/pustules
4	Severe	Numerous small and/or large papules/pustules

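### Should the modified full analysis set as randomised, rather than the full analysis set as treated, be the primary analysis after the kit misallocation?

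*SAP*

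**What the plan says.** Protocol 16.1 and SAP 4.5 report a "treatment kit misallocation that occurred for 15 patients out of the initial 30 patients randomized". In response the sample size was "increased to a total of 201 patients (67 in each treatment group) to mitigate the impact on the statistical power"; the earlier target was 171, or 57 per arm.

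The same event set the grouping rule. Protocol 16.2.3 gives the reason, "To mitigate the impact of the treatment kit misallocations", and SAP 5.4.4 repeats it: "the primary statistical analysis on the FAS will be performed according to the actual treatment received". Both sections say openly that this is not the intention-to-treat grouping.

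Protocol 16.3 continues: "In addition, two sensitivity analyses will be implemented for the primary analysis". SAP 7.1 plans the same two. One is the full analysis set (FAS) as randomised. The other is the mFAS as randomised, which leaves out the first 30 patients randomised, whichever kit they received.

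SAP 3.2.1 ties the claim to the co-primary endpoints: "Success of the study will be declared in any of the active treatment groups if both the co-primary efficacy endpoints will be satisfied".

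For the per protocol (PP) set, SAP 5.4.6 excludes major deviations that could affect results and groups by actual treatment. SAP 5.4 and 6.3 settle the populations blind, and 6.3 names intake of a non-assigned treatment among the deviations to be determined. SAP 6.8 checks bottle numbers after database lock and unblinding, and calls any wrong treatment taken a major deviation.

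**The concern.** Grouping by treatment received gives up the protection of randomisation for the 15 affected patients. It is unbiased only if the kit error was unrelated to prognosis, and the available text states neither the cause of the error nor the arms involved. Because study success is declared on the co-primary endpoints, the analysis ranked first carries the headline.

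An alternative seems ready to hand. The 30 added patients equal in number the 30 that the mFAS removes. The mFAS excludes by order of randomisation, not by kit, so it remains a randomised comparison whatever caused the error, and it is about as large as first planned. Ranking it second looks like an unforced departure from randomisation.

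The PP set raises a smaller worry. If a wrong kit is a major deviation established only after unblinding, it is unclear how membership can be settled blind, and whether wrong-kit patients stay in a set that is grouped by actual treatment.

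**Working it through.** **Inputs.** From Protocol 16.1 and SAP 4.5: 51 per arm before dropout, about 10% dropout, 171 then 201 randomised, 15 misallocations among the first 30. From Protocol 16.3.1: two-sided 5% tests. Effect sizes and planned power are redacted, so 80% and 90% power at 51 per arm are assumed for illustration.

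**The plan's own figure.** 51/0.9 = 56.7, rounded up to 57; 57 × 3 = 171. Reproduced.

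**Size of the mFAS.** 201 − 30 = 171, or 57 per arm. After 10% loss, 57 × 0.9 = 51.3 per arm, against 51 planned. This is a ceiling, because SAP 5.4.4 also requires a dose and a post-baseline assessment. The FAS after 10% loss has 67 × 0.9 = 60.3 per arm.

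**How many patients the grouping affects.** 15/201 = 7.5%. The other 186 are grouped identically either way.

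**Possible bias as treated.** Assume 5 wrong-kit patients in each arm of 67, with mean prognosis differing by d SD between those on active and those on placebo. Bias = d × 5/67. Standard error = √(2/60.3) = 0.182 SD.

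| d (assumed) | Bias (SD) | Bias (SE) | Actual size of a 5% test |
|---|---|---|---|
| 0.25 | 0.019 | 0.10 | 5.1% |
| 0.5 | 0.037 | 0.20 | 5.5% |
| 1 | 0.075 | 0.41 | 6.9% |

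These are rates for one endpoint and ignore the covariate adjustment in SAP 7.2. Success needs both co-primary endpoints, so they are not the error rate of the success claim.

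**Cost of making the mFAS primary.** Standard error ratio = √(67/57) = 1.084, about 8% larger. For power, the noncentrality is 1.96 + z(power), multiplied by √(n/51), with n = 51.3 for the mFAS and 60.3 for the FAS.

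| Analysis | If 80% planned | If 90% planned |
|---|---|---|
| mFAS as randomised | 80% | 90% |
| FAS as treated | 86% | 94% |

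The loss is about 6 or 4 points. The first 30 also include 30 − 15 = 15 patients with no reported misallocation, who would leave the primary analysis.

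**FAS as randomised.** If the 15 errors fall 5 per arm, half going to each other arm, the expected active-placebo difference is 1 − 7.5/67 = 0.888 of the true one. Power is then about 77% or 88%. A diluted comparison has its own drawback, so none of the three analyses is best on every count.

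**PP set.** Set side by side, SAP 6.3 determines wrong-treatment intake and evaluability before unblinding, while SAP 6.8 verifies bottles afterwards. The 15 known cases can be handled at the blind review. Only cases first found at the later check fall between the two sections.

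**The case for a change.** The best argument for re-ranking is that it costs no new analysis. The mFAS as randomised is already programmed, is about the size the trial was first designed for, and needs no assumption about the cause of the error, provided no further kit errors occurred. As-treated grouping does need that assumption. It can also change after unblinding if the SAP 6.8 check finds new errors, whereas the randomised grouping is fixed by the list. All of this is true, and a statistician who had put the mFAS first would have made a sound choice.

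It does not show that the sponsor's choice is wrong. Protocol 10.3 has the system issue a "kit number based on a pre-defined randomisation list", and Protocol 10.6 keeps "both the Investigator and the patient will be unaware of the treatment being dispensed in each case". A kit error under those conditions has no evident route to prognosis. The unstated cause is missing detail, and it may stand in material withheld from the public copy. Regrouping after the bottle check would follow mechanically from bottle numbers, not from judgement about outcomes. The mFAS result will be reported in any case, so a conflict with the primary result would be visible.

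On the PP set, the mismatch between SAP 6.8 and SAP 5.4 and 6.3 is real. It is confined to newly found cases in a supportive set, and SAP 6.3 refers the process for identifying deviations to a separate document.

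**Conclusion.** No change to the plan is needed. The ranking trades a more precise comparison, which depends on the kit error being unrelated to prognosis, against a randomised one with a standard error about 8% larger. Under the assumed 80% or 90% planned power, the mFAS gives up about 4 to 6 points. In return it guards against a bias that is not shown and that would move a 5% test to 5.1% to 5.5% at a prognosis gap of 0.25 to 0.5 SD; only a gap of 1 SD takes it to 6.9%. The bias figures assume 5 wrong-kit patients per arm. For a phase IIa proof-of-concept trial that discloses the choice, gives its reason and plans both as-randomised analyses, this is within reasonable judgement. The analyses already planned let a reader set the mFAS result beside the primary one and weigh any disagreement.

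The PP point is a small gap in written detail. The blind review can settle the 15 known cases, and what remains concerns only late-found cases in a supportive analysis.

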5.4.5 Modified Full Analysis Set

Modified Full Analysis Set (mFAS) is defined as all patients in the FAS excluding the initial 30 patients randomized.

The analysis on the mFAS will be performed according to the "randomized" treatment.

5.4.6 Per Protocol Analysis Set

Per Protocol Analysis (PP) set is defined as all subjects in the FAS who fulfil the study protocol requirements with no major deviations that may affect study results.

Analysis on the PP set will be performed according to the actual treatment received. Patients randomized to a wrong stratification factor level will not be excluded from the PP set and will be analyzed according to the actual stratum (not the randomized one).

